**Funder: N/A**

No funding required (VR headset loaned by Sync VR Medical).

This protocol describes the virtual reality technology during outpatient hysteroscopy study and provides information about procedures for entering participants. . Every care was taken in its drafting, but corrections or amendments may be necessary. These will be circulated to investigators in the study. Problems relating to this study should be referred, in the first instance, to the Chief Investigator.

This study will adhere to the principles outlined in the UK Policy Frame Work for Health and Social Care Research. It will be conducted in compliance with the protocol, the Data Protection Act and other regulatory requirements as appropriate.

**GLOSSARY OF ABBREVIATIONS**

3D US	Three dimensional Ultrasound
VR	Virtual reality
OPH	Outpatient Hysteroscopy
NHS	National Health Service

**KEYWORDS**

Virtual reality technology, outpatient hysteroscopy, pain, anxiety. Endometrial receptivity; endometrial receptivity array; mRNA expression; uterine fibroids; uterine septum; recurrent miscarriage; subfertility; implantation; window of implantation; metroplasty; myomectomy

**STUDY SUMMARY**

**TITLE** Does Virtual Reality Technology Reduce Pain and Anxiety During Outpatient Hysteroscopy? A Randomised Controlled Trial

**DESIGN** Randomised controlled trial

**AIMS** To evaluate whether the use of virtual reality technology can reduce pain and anxiety during outpatient hysteroscopy procedures.

**OUTCOME MEASURES** Primary outcome measures are patient reported NRS (numeric rating score) for pain and anxiety.  
Secondary outcome measures will be length of procedure, complication rate, reported side effects, procedure completion or if stopped, hysteroscopy findings and type of procedure performed.

**POPULATION** Women aged referred from general gynaecology clinics for outpatient hysteroscopy procedures.

**ELIGIBILITY** Inclusion criteria are age 18-70, capacity to give informed consent and cognitive and linguistic ability sufficient to understand and fill out the NRS questionnaire. Exclusion criteria are epilepsy or severe vertigo, blindness or significant hearing impairment and recent facial injury/burn

**DURATION** 1 year

# 1. INTRODUCTION

## 1.1 BACKGROUND

Hysteroscopy is a very common gynaecological procedure where a camera attached to a thin scope is passed into the uterus via the vagina and cervix in order to obtain views of the inside of the uterus. Hysteroscopy is used for the diagnosis and management of a variety of benign and conditions as well as the diagnosis of uterine cancer. It can be performed under general anaesthetic or in an outpatient setting without formal anaesthetic. The latter has several advantages when compared to hysteroscopy with general anaesthesia as it avoids the additional risk of general anaesthesia, has a quicker recovery time, shorter hospital stay and reduced cost. Outpatient hysteroscopy (OPH) is generally well tolerated although some women will experience significant pain and pain is one of the most common reasons for failure to complete the procedure.

As pain is one of the leading reasons for procedure failure, finding ways to reduce pain and anxiety is of critical importance. The optimal method of controlling pain and anxiety during outpatient hysteroscopy is poorly understood and hotly debated. Options include sedation, local anaesthetic, analgesics including paracetamol, non-steroidal anti-inflammatory medication, opioids, Entonox and various distraction techniques. There is a wide variation of clinical practice between different units within the UK due to a paucity of good quality evidence informing best practice. Conventional therapy, as recommended by the Royal College of Obstetricians and Gynaecologists, involves the use of simple pain killers taken prior to the procedure and sometimes local anaesthetic during the procedure if dilatation of the cervix is required (RCOG 2011).

Virtual reality (VR) technology is a relatively new and promising technology which if used as a distraction technique, may be able to reduce pain and anxiety experienced from a wide range of medical procedures. Virtual reality (VR) is a human–computer interface that provides users with various physical sensations (e.g., visual, haptic, auditory) to increase realism in the virtual world (Seth et al. 2011). This heightened sense of realism produces a phenomenon known as “presence,” which refers to the user’s authentic experience of being in the virtual world as a result of visual or auditory displays generated by a computer (Barfield and Hendrix 1995). VR’s ability to provide users with highly realistic immersive experiences can be used to for a variety of medical indications including distraction from uncomfortable or painful procedures.

To date VR has been used in a wide variety of inpatient and outpatient clinical scenarios to reduce pain and anxiety including simple blood tests, ENT procedures and minor gynaecological procedures such as hysterosalpingograms (Chan et al 2018, Wang et al 2020 and Ahmadpoura et al 2019). However, currently, to the best of our knowledge, there is only one relatively small-scale trial investigating the use of VR in an outpatient hysteroscopy setting (Deo et al 2020) meaning further studies are urgently needed to clarify the situation.

## **1.2 RATIONALE FOR CURRENT STUDY**

The purpose of this study would be to determine if the use of VR technology can reduce pain and anxiety experienced by patients during outpatient hysteroscopy procedures when compared to standard pain management.

The optimal method of controlling pain and anxiety during outpatient hysteroscopy is poorly understood and there is a wide variation in clinical practice. This study aims to test whether VR technology could reduce pain and anxiety as a relatively simple and safe adjunct to conventional pain management. Although VR has been used in a variety of clinical settings to date, there is only one previous study investigating the use of VR in an outpatient hysteroscopy setting (Deo et al 2020). This existing trial established that the use of VR is feasible in the OPH setting and that it was effective with significant improvements in patient reported anxiety and pain scores compared to conventional pain management. However, as the authors themselves acknowledge, it involved relatively small numbers (20 patients in control and intervention group respectively). The rationale of this study would be to build upon this evidence by performing the first large scale adequately powered randomised control trial of the use of VR technology in this setting.

We hypothesise that the use of VR technology will significantly improve pain and anxiety when compared to conventional pain management. Finding additional low risk ways of improving pain and anxiety during OPH is of critical importance in order to improve patient experience and the success rate of the procedure as pain is a major reason for unsuccessful OPH procedures.

## **2. STUDY OBJECTIVES**

The primary objectives of this study are to determine if:

- 1) VR technology can reduce pain during outpatient hysteroscopy?
- 2) VR technology can reduce anxiety during outpatient hysteroscopy?

The secondary objectives of this study are to determine if:

- 1) The use of VR technology feasible during outpatient hysteroscopy?
- 2) The use of VR during outpatient hysteroscopy reduces the procedure failure rate?
- 3) The use of VR increases the outpatient hysteroscopy appointment time?

### 3. STUDY DESIGN

The study design is an unblinded randomised controlled trial. This study design was chosen as it will provide the best quality of evidence with reduced bias compared to other study designs. A randomised controlled trial is also very feasible in this scenario. Neither the researchers nor the participants will be blinded as to which study arm they are in, as it would be impractical to do so with a VR headset used in the intervention group. The study will be adequately powered with a power calculation based upon findings from previous studies, meaning at least 40 patients will be included in each arm (at least 80 patients in total).

Patients will be randomly allocated by computer allocation to either the intervention or the control group. The intervention group will undergo OPH with standard care plus the use of VR technology administered through a headset with the option of wearing headphones (at the patient's discretion) or having the accompanying sound played aloud. The control group will undergo outpatient hysteroscopy with standard care. Standard care in this unit is in line with the RCGOG guidelines and involves advising patients to take ibuprofen and/or paracetamol one hour prior to their procedure unless there are contraindications. Local anaesthetic intracervical block is used at the discretion of the operator and is usually used if dilatation of the cervix is required.

The primary outcome measure will be the reported NRS (numeric rating score) score which is validated score to assess pain and anxiety levels with values from 0-11. The patient will be asked to fill out the NRS score prior to the hysteroscopy and following the hysteroscopy prior to leaving the clinic.

Secondary outcome measures will be length of procedure, complication rate, reported side effects, procedure completion, hysteroscopy findings and type of procedure performed (for example if purely diagnostic or if any operative procedures are performed).

Participants will be recruited from the general gynaecology clinics. Only patients who have already opted to undergo outpatient hysteroscopy will be invited to take part in the study and they will be made aware of the study at the time of the clinic appointment or shortly after. Interested parties will then be contacted by the research team to discuss the study in more detail at a time which is convenient for the patient. Written consent to enter the study will be sought from the participant in advance of their procedure and only after a full explanation has been given. The patient will be offered a study information leaflet. Whilst waiting for their hysteroscopy procedure, the patient will be offered a face-to-face appointment with a member of the research team to discuss the study and sign the written consent form if they wish to participate in the study. If it is more convenient for the patient, and to avoid unnecessary additional appointments for the patient, they may prefer to discuss the study and go through the consent by phone before confirming consent on the day of the procedure. Patients will have time to consider whether to take part in the study prior to their procedure day and will be informed that they can withdraw consent for participation in the study at any time. Participating or not participating in the study will have no effect on the timing of the outpatient hysteroscopy or the type of procedure performed. Patients will have the opportunity to choose which virtual reality scenario they wish to experience during the procedure (choice of 4 scenarios from beach, space, underwater and zen four seasons).

At the time of their hysteroscopy. The patient will fill out the pre-procedure NRS score prior to entering the hysteroscopy room. The patient will then enter the outpatient hysteroscopy room where there will be the hysteroscopy team consisting of the lead hysteroscopist and the assistant, and also a single member of the research team who will have taken the study consent from the patient prior to their procedure. Following discussion with the hysteroscopist as usual, the patient will prepare for the procedure and position themselves on the procedure couch. Once comfortable, the member of the research team will help the patient to put on the VR headset (See appendix 1), and if the patient wishes, headphones. The virtual reality software will then start running and is controlled by the research team member, the software will run for the length of the procedure. The hysteroscopy team will be preparing the equipment as the virtual reality software is running. The member of the research team will remain in the room throughout the procedure to troubleshoot any issues with the headset or software and if necessary to stop the VR program. Following completion of the procedure the patient will fill out a NRS score prior to going home.

The VR software involves breathing exercises, relaxing music and a distracting immersive walk through a virtual environment. The scenario will be started and subsequently controlled by a member of the research team operating a tablet device. The hysteroscopy team will perform the procedure in exactly the same way as they would normally and any clinical decisions regarding potential procedures such as polypectomy, discontinuing or proceeding with the hysteroscopy will be made by the hysteroscopy team along with the patient in the usual way without any input from the research team member.

Maintaining appropriate clinical hygiene is of critical importance as the same headset will be used for different patients. The headset can be easily and effectively cleaned between use and the manufacturer (VR medical) provides a recommended cleaning regimen which we will use for the trial. After use, the VR device and controller should be cleaned with a damp microfibre cloth and disinfectant wipe, both the parts that have been in contact with the skin and the headbands.

The timetable for the project is expected to run as follows. Three months for preparation and obtaining ethical approval. Recruitment is expected to start following this and we would expect to obtain the required number of participants by 3 months based on the average referral rate for outpatient hysteroscopy in the unit being 150 patients per month and a 20% study participation rate. Data analysis and preparing the final report would take a further 3 months.

Results will be recorded onto a pseudoanonymised database. Information will be collected from patients notes and imaging reports. Each patient will be allocated a study number and for each the following will be recorded:

- Age
- Parity
- Symptoms and duration
- Past medical history and co-morbidities
- BMI
- Previous surgery
- Current medication and medication used within the last 6 months
- Pain NRS (numeric rating score)
- Anxiety NRS

Length of hysteroscopy procedure  
Time in Outpatient Procedure room  
Procedure successfully completed (or not) and reason for failure if appropriate  
Complications  
Hysteroscopy findings  
Type of hysteroscopic procedure performed

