**CI email (and contact details below)**

## 6. ASSESSMENT AND FOLLOW-UP

Definition of end of study: when final participant has been recruited within 1 year study period and has had filled out their post procedure NRS questionnaire. Incidental findings are not expected in this study. Any clinically relevant incidental findings that do occur during this study will be reported to the GP for ongoing care as necessary.

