## **7. STATISTICS AND DATA ANALYSIS**

Normally distributed data will be analysed using IBM SPSS software. Comparisons will be done with between intervention group and controls with a p value less than 0.05 used to indicate statistical significance.

Means NRS scores will be compared between the 2 groups using the unpaired student's T test.

Data and all appropriate documentation will be stored for a minimum of 5 years after the completion of the study, including the follow-up period.

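### Is a floor of 40 per arm too small for the two primary NRS comparisons, when the stated year could hold more patients?

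*Combined protocol and SAP*

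**What the plan says.** Section 3 (Study design) says the trial will have adequate power from a calculation resting on earlier studies, "meaning at least 40 patients will be included in each arm (at least 80 patients in total". No inputs to that calculation appear there or in section 7. Section 7 specifies an unpaired t test on mean NRS scores, "with a p value less than 0.05 used to indicate statistical significance". The study summary names two primary outcomes, pain and anxiety.

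Section 1.2 describes one earlier trial of VR in outpatient hysteroscopy. It says that "it involved relatively small numbers (20 patients in control and intervention group respectively", and that VR was "effective with significant improvements in patient reported anxiety and pain scores". It presents VR as a "relatively simple and safe adjunct to conventional pain management".

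The timetable in section 3 allows three months for preparation and expects recruitment to finish within three months, on the basis of "150 patients per month and a 20% study participation rate". It then says: "Data analysis and preparing the final report would take a further 3 months". The study summary gives a duration of one year, and section 6 defines the end of study as "when final participant has been recruited within 1 year study period" and the post-procedure questionnaire is complete.

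**The concern.** A claim of adequate power without a target difference or SD cannot be checked. Solved backwards, 40 per arm is sensitive only to fairly large effects, and nothing in the documents says that smaller ones are unimportant for a low-risk addition to standard care. If the true effect on pain were 0.4 SD, the trial would have a 58% chance of a non-significant result, which readers could take to mean that VR does not work.

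The margin also looks thin against the one earlier trial described. A significant result with 20 per group needs a large observed effect, and small significant trials tend to overstate the truth. Meanwhile the timetable adds up to nine months and the study has a year, so the plan seems to leave patients unused.

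**Working it through.** **Inputs from the documents.** 40 per arm (section 3); unpaired t test at 0.05 (section 7); 150 referrals a month with 20% participation, and three months each for preparation, recruitment and analysis (section 3); one year (study summary, section 6).

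**Assumed.** Two-sided test, 80% power, equal allocation, effects of 0.3 to 0.64 SD. None of these is stated.

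**The plan's own figure.** 40 per arm cannot be reproduced, because its inputs are not given.

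**Detectable difference at 40 per arm.** d = (z for 0.975 + z for 0.80) × √(2/n) = (1.960 + 0.842) × √(2/40) = 2.802 × 0.2236 = 0.626 SD. The exact noncentral t gives 0.634 SD. With 10% loss (36 per arm) it is 0.67 SD; at 90% power with 40 per arm, 0.734 SD. A one-sided 5% test gives 0.556 SD (normal approximation).

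**Power (noncentral t, two-sided 5%).**

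| Per arm | 0.3 SD | 0.4 SD | 0.5 SD | 0.64 SD | Detectable at 80% |
|---|---|---|---|---|---|
| 40 | 26% | 42% | 60% | 81% | 0.63 SD |
| 45 | 29% | 47% | 65% | 85% | 0.60 SD |
| 64 | 39% | 61% | 80% | 95% | 0.50 SD |
| 90 | 52% | 76% | 92% | 99% | 0.42 SD |

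**The earlier trial.** If it used a two-sided 5% t test, the smallest significant observed effect was t(0.975, 38 df) × √(2/20) = 0.640 SD. That effect needs 39.3 per arm at 80% power and 52.3 at 90%. So 40 is a ceiling only if both that test and an 80% target are assumed. The documents give neither, nor that trial's effect. Section 3 also refers to previous studies in the plural, so the origin of 40 is unknown.

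**Room in the year.** Recruitment is 150 × 0.20 = 30 a month, so 80 patients take 80/30 = 2.7 months. The number that fits depends on how the year is read:

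- The planned three months: 90 patients, 45 per arm.
- A year that includes preparation and analysis: 12 − 3 − 3 = 6 months, 180 patients, 90 per arm.
- A year that ends at the last questionnaire but includes preparation: 9 months, 270 patients, 135 per arm.
- A year of recruitment only: 360 patients, 180 per arm.

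**Cost of enlarging, counting analysis inside the year and allowing 10% loss.** For 128 analysed: 128/0.9 = 142.2, so 143 recruited; 143/30 = 4.8 months, and 3 + 4.8 + 3 = 10.8 months in all. For 180 analysed: 180/0.9 = 200 recruited; 200/30 = 6.7 months, and 12.7 in all, which is over the year.

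**What the spare months protect.** If participation were 10%, recruitment would be 15 a month. Then 80 patients take 80/15 = 5.3 months, and 3 + 5.3 + 3 = 11.3 months: the floor is still reached within the year.

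**What a non-significant result would show.** The 95% interval for the mean difference at 40 per arm has half-width t(0.975, 78 df) × √(2/40) = 1.991 × 0.2236 = 0.445 SD. An observed difference of 0.4 SD would give about −0.05 to 0.85 SD, which plainly does not exclude a useful effect.

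**The case for a change.** The strongest case for a change is that section 1.2 offers this as the first large, properly powered trial in the setting, and then gives a size that nobody can verify. Under plausible assumptions that size would miss a moderate effect about as often as it finds one. At 0.4 SD, going from 40 to 90 per arm cuts the chance of a non-significant result from 58% to 24%. The sample size is also open-ended: there is a floor, no stated maximum, and an end of study tied to the last participant without a number.

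Part of this stands. The inputs are missing, and the sensitivity figures are right. The rest depends on effect sizes that the documents do not support. The inference from the 20-per-group trial is conjecture about how 40 was obtained. The larger sizes do not settle the 0.4 SD example either: 128 patients give 61% and 180 give 76%, and 80% needs 100 per arm. Choosing among them is a matter of preference. The unused months can fairly be read as contingency. As 40 is a minimum, the 0.63 SD figure is the least favourable case if all are analysed; the plan's own three months would give 45 per arm and 0.60 SD.

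**Conclusion.** No change follows. Under a two-sided 5% t test, 40 per arm has 80% power from about 0.63 SD, or 0.67 SD with 10% loss. That describes limited sensitivity. It does not contradict anything the plan commits itself to, because no effect size, power or minimum important difference is stated for the design to miss.

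Asking for 48 to 100 more patients would replace one unsupported target with another. The gain is real only if the true effect lies below about 0.63 SD. The cost is a longer headset loan and more time for a research team member in the procedure room, and 180 analysed does not fit the year once 10% loss is allowed on the reading that gave 90 per arm. Keeping a floor of 40, with slack against slow recruitment, is a fair trade-off.

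The unreported inputs are a gap in documentation, and no stated rule has been shown to give a wrong result because of it. Any reader can derive the detectable difference from the size and the test. In the report, analysts can be expected to give the number recruited and the mean difference with its confidence interval, which guards against reading a non-significant result as evidence of no effect. These conclusions rest on the two-sided test, 80% power and equal arms assumed above.

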### **3.1 STUDY OUTCOME MEASURES**

The primary outcome measure will be the reported NRS (numeric rating score) score which is validated score to assess pain and anxiety levels with values from 0-11. The patient will be asked to fill out the NRS score prior to the hysteroscopy and following the hysteroscopy prior to leaving the clinic.

Secondary outcome measures will be length of procedure, complication rate, reported side effects, procedure completion, hysteroscopy findings and type of procedure performed (for example if purely diagnostic or if any operative procedures are performed).

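### Does the pain comparison need planned data on intracervical block, which an operator who can see the headset gives at discretion?

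*Combined protocol and SAP*

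**What the plan says.** Section 3 defines the control arm as standard care and the intervention arm as standard care plus VR. Standard care includes advice to take ibuprofen and/or paracetamol an hour beforehand. It also includes a local anaesthetic option: "Local anaesthetic intracervical block is used at the discretion of the operator and is usually used if dilatation of the cervix is required".

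On blinding, section 3 states: "Neither the researchers nor the participants will be blinded as to which study arm they are in". That sentence does not name the operator. However, the account of the procedure has the hysteroscopy team in the room preparing equipment while the VR programme runs, so the operator will know the arm. The same account says: "The hysteroscopy team will perform the procedure in exactly the same way as they would normally".

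On data, section 3 says "Information will be collected from patients notes and imaging reports" and then lists the items to be recorded. The nearest ones are "Current medication and medication used within the last 6 months" and the type of hysteroscopic procedure. Block and cervical dilatation are not listed. Section 3.1 gives the other outcomes: "Secondary outcome measures will be length of procedure, complication rate, reported side effects, procedure completion, hysteroscopy findings and type of procedure performed". Section 7 provides in general terms for comparisons between the two groups at p < 0.05, and names one method: "Means NRS scores will be compared between the 2 groups using the unpaired student's T test".

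**The concern.** The primary outcomes include pain, and block is a pain treatment given at the discretion of someone who can see the allocation. In an open trial that is the usual route by which co-treatment drifts apart between arms. An operator might hold back a block because the patient seems distracted, or give one sooner to a control patient. The statement that the team works as normal is an intention, and normal practice is itself discretionary.

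If block use differed, a reader could not tell whether a pain difference, or its absence, came with more, less or similar local anaesthetic. Section 1.2 presents VR as a "relatively simple and safe adjunct to conventional pain management", so reduced need for block would be a benefit in its own right, and no listed outcome is aimed at it. The clause in section 8.2 on recording reasons does not help: it covers treatment alternative to the protocol, and block is already part of standard care.

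**Working it through.** **1. What is and is not covered.**

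| Item | Recorded-data list (section 3) | Outcomes (section 3.1) | Other source |
|---|---|---|---|
| Intracervical block | Not named | Not named | Patients' notes |
| Cervical dilatation | Not named | Not named | Patients' notes |
| Same-day tablets | Read literally, within medication used in the last 6 months; no same-day prompt | Not named | Patients' notes |

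The gap is the absence of a named item for block and dilatation. Same-day tablets fall within an existing item, and section 7 allows by-arm comparison of whatever is recorded.

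**2. Which effect is estimated.** Let D be the direct effect of VR on mean pain, Δ the between-arm difference in the proportion given a block, and b the effect of a block on pain. With b taken as constant, the difference in means is approximately D + Δ × b. For the question of standard care plus VR against standard care, the whole sum is the target. The term Δ × b would be bias only for a different question: the effect of VR with block use held fixed.

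**3. Size of Δ × b.** The documents give no value for Δ or b, so these are assumptions.
- 0.10 × 1 = 0.1 points; 0.20 × 2 = 0.4 points.
- With Δ as large as 0.30: 0.30 × 2 = 0.6 points.

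**4. What 40 per arm can detect.** Section 3 gives at least 40 per arm but no effect size, SD or power, so that figure cannot be reproduced. For a two-sided t test at 0.05 with 80% power, the detectable difference is 0.634 × SD: 1.27 points (SD 2), 1.59 (SD 2.5) and 1.90 (SD 3). The SDs are assumed.

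**5. Effect on the test if D = 0.** The shift is divided by SD × √(2/40) and the two-sided rejection rate taken from the normal approximation.

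| Shift | SD 2 | SD 2.5 | SD 3 |
|---|---|---|---|
| 0.1 | 5.6% | 5.4% | 5.3% |
| 0.2 | 7.3% | 6.5% | 6.0% |
| 0.4 | 14.5% | 11.0% | 9.2% |
| 0.6 | 26.9% | 18.9% | 14.5% |

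**6. What a by-arm table of block use could show.** If block use is p in both arms, the 95% half-width for the risk difference is 1.96 × √(2p(1−p)/40).
- p = 0.2: 1.96 × √0.0080 = 17.5 points
- p = 0.3: 1.96 × √0.0105 = 20.1 points
- p = 0.5: 1.96 × √0.0125 = 21.9 points

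The exact binomial probability of a gap of at least 10 points (4 of 40) with no true difference is 0.33, 0.39 and 0.43 respectively. Power to detect a true 20-point difference is 45% (50% v 30%) or 50% (40% v 20%), using the pooled-variance normal approximation.

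**The case for a change.** The strongest case for a change is that recording block costs almost nothing on the day, whereas retrieval from notes depends on what was written and may be less complete in one arm. Validity of the randomised comparison does not settle interpretation: no pain difference with less block under VR means something other than no difference with equal block. Operators may also act differently because they are in a trial, and that behaviour would not carry over to routine use. With the larger assumed inputs (30 points, 2 score points, SD 2), block alone would produce a significant result in 27% of trials with no direct VR effect.

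Part of this stands. Block and dilatation are not itemised, and observed counts by arm would help a reader. The rest is weaker. The 27% needs every assumption at its extreme, and nothing in the documents suggests that block depends on arm: its usual trigger is cervical dilatation, a procedural need. The table would show what happened in these patients, but at this size could seldom establish that use was alike or different. It could not support adjustment either, because block is given after randomisation and may respond to the arm. The primary analysis would be the same with or without the data.

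**Conclusion.** The omission is real but requires no change. Followed as written, the plan gives a sound comparison of the two care packages, and any VR-driven change in block use belongs to that comparison. The assumed shift of 0.1 to 0.4 points is well below the detectable 1.27 to 1.90 points; even 0.6 remains below it. These sizes rest on assumed block use, block effect and SD, none of which the documents give, and on a two-sided 5% test.

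The missing counts are descriptive. Analysts can seek block and dilatation in the notes, already a stated source, and tabulate them by arm without a test, together with same-day tablets from the medication item. A data-form entry for each would be a convenience. If the notes prove incomplete, the report should say that block use by arm is unknown; the primary result is unaffected.
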